### 1.2 Secondary Aims

- 1.2.1 To determine the percentage of eligible patients for whom a suitable LMP-specific T-cell product derived from a Third Party LMP-specific T-cell bank is available.
- 1.2.2 To estimate the response rate (RR) to three doses of RTX as single agent in children and young adults with newly diagnosed or relapsed EBV-Positive CD20-Positive PTLD after solid organ transplantation (SOT).
- 1.2.3 To estimate the 2-year event-free survival (EFS) of children and young adults with newly diagnosed, refractory or relapsed EBV-Positive CD20-Positive PTLD after SOT treated with RTX and/or LMP-specific T cells.
- 1.2.4 To estimate overall survival (OS) of children and young adults with newly diagnosed, refractory or relapsed EBV-Positive CD20-Positive PTLD after SOT treated with RTX and/or LMP-specific T cells.
- 1.2.5 To estimate the RR to LMP-specific T cells of newly diagnosed (without complete response to Course RTX1), refractory, and relapsed children and young adults with EBV-Positive CD20-Positive PTLD.
- 1.2.6 To estimate progression-free survival (PFS) of children and young adults with newly diagnosed, refractory or relapsed EBV-Positive CD20-Positive PTLD after SOT treated with RTX and/or LMP-specific T cells.
- 1.2.7 To describe the toxicity of Third Party LMP-specific T cells in children and young adults with newly diagnosed, refractory or relapsed EBV-Positive CD20-Positive PTLD after SOT treated with RTX and/or LMP-specific T cells.
- 1.2.8 To validate that absence of EBV viremia correlates with RR, EFS and OS.

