3.2.2.2.1 CD20 positive

3.2.2.2.2 EBV positive by EBER in situ hybridization (preferred) and/or LMP immunoperoxidase staining.

3.2.2.3 There must be evaluable disease at study entry either by imaging or by serial endoscopic biopsies.

Note: as indicated in [Section 10.2.5.1](#) a measurable node must have an LDi (longest diameter) greater than 1.5 cm. A measurable extranodal lesion should have an LDi greater than 1.0 cm. All tumor measurements must be recorded in millimeters (or decimal fractions of centimeters).

3.2.2.4 Patients must be considered medically refractory to decreased immunosuppression (50% or greater reduction) for at least 1 week or there must be documentation in the medical chart that decreased immunosuppression would be associated with an unacceptable risk of rejection.

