##### 4.1.2.2 **Arm LMP-TC**

**Cohort A:** Newly diagnosed patients who do not achieve a complete response (CR) after Induction will be assigned to Arm LMP-TC.

**Cohort B:** All relapsed patients will be assigned to Arm LMP-TC after induction regardless of response.

**Cohort C:** All patients with refractory disease who have received rituximab (or biosimilar) within 90 days according to institutional guidelines are assigned to Cohort C and proceed directly to Arm LMP-

TC at enrollment.

Patients assigned to Arm LMP-TC without a suitable LMP-specific T-cell product will go off protocol therapy. Further treatment with chemotherapy is at the discretion of the treating physician.

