## 9.3 Methods of Analysis

For the primary endpoint, the point estimate of the proportion successfully matched and treated (among all 3 Cohorts combined) will be the uniformly minimum variance unbiased estimator, and an exact one-sided binomial 95% confidence interval (adjusted for the interim analysis by the method of Jung and Kim)[37](#) will be used to get a lower bound for the actual rate of successful treatments as defined in the primary objective.

For the secondary endpoints:

- The proportion of eligible patients who are successfully matched will be assessed using the uniformly minimum variance unbiased estimator for the proportion and an exact one-sided binomial 95% confidence interval (adjusted for the interim analysis by the method of Jung and Kim) to get a lower bound for the actual rate.
- PFS (defined as time to first occurrence of progression or death (events) or loss to follow-up or survival to analysis date (non-events)), EFS (defined as time to first occurrence of relapse, second/secondary malignant neoplasm (SMN), death (events) or loss to follow-up or survival to analysis date (non-events)), and OS (defined as time to death (event) or loss to follow-up or survival to analysis date (non-events)) will be assessed using Kaplan-Meier estimates, both for all patients combined and also separately in each Cohort. Aim 1.2.8 will be assessed using the Log-Rank test for EFS and OS and the exact conditional test of proportions (Fisher's Exact test) for RR, both for all patients combined and stratified by Cohort.
- Response rates will be assessed using exact two-sided binomial 95% confidence intervals to get estimates of the response rate. Aim 1.2.2 will be evaluated in Cohorts A and B only (combined and separately), with response classified by comparing disease evaluation at the Week 3 evaluation to the baseline of disease evaluation at study entry using the criteria in Section 10.2. Patients with CR will be considered responders. For Aim 1.2.5, response will be classified by comparing disease evaluation at the Week 6 of LMP-CT1 evaluation to the baseline of disease evaluation at the Week 3 evaluation using the criteria in Section 10.2, both in all Cohorts combined and in each Cohort separately. Patients with CR or PR will be considered responders.
- Toxicities will be described using descriptive statistics. Toxicity monitoring and analysis will be performed based on "as treated".

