#### 9.4 Evaluability for Response

Eligible patients assigned to Arm LMP-TC will be considered evaluable for the primary endpoint (percentage successfully matched and treated). All 3 Cohorts will be combined into a single set of patients for the analysis.

All eligible patients will be evaluable for Aims 1.2.1, 1.2.8, and 1.3.2. For Aim 1.2.1, all patients who submit HLA typing by the end of the trial will be evaluable, regardless of the timing of the submission.

Any eligible patient who receives at least one dose of RTX will be considered evaluable for Aims 1.2.2–1.2.4 and 1.2.6.

Any eligible patient who receives at least one dose of LMP-specific T cells will be considered evaluable for Aims 1.2.5, 1.2.7, 1.3.1, and 1.3.3.

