#### 10.2.4 Definitions

10.2.4.1 Evaluable for toxicity: A patient will be considered for toxicity monitoring if the patient is eligible and one of the following occurs: (1) completes one course of protocol therapy; (2) dies on protocol therapy for a reason considered possibly, probably, or likely related to protocol therapy; or (3) is removed from protocol therapy because of an adverse

experience possibly, probably, or likely related to one of the agents.

10.2.4.2 **Evaluable for objective response:** Only those patients who have measurable disease present at baseline and have received at least one dose of protocol therapy will be considered evaluable for response. These patients will have their response classified according to the definitions stated below. (Note: Patients who exhibit objective disease progression prior to the end of Course 1 will also be considered evaluable.)

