### 10.2.7 Response Criteria

#### 10.2.7.1 Evaluation of Measurable Disease

Complete Response (CR): *Disappearance of all disease.* CT or MRI should be free of residual mass or evidence of new disease. FDG-PET should be negative.

CR unconfirmed (Cru): Residual mass is negative by FDG-PET; no new lesions by imaging examination; no new and/or progressive disease elsewhere

Partial Response (PR): 50% decrease in SPD (the sum of the products of the largest diameter and the perpendicular diameter for a tumor mass) on CT or MRI; FDG-PET may be positive (Deauville score or 4 or 5 with reduced lesional uptake compared with baseline); no new and/or PD; morphologic evidence of disease may be present in BM if present at diagnosis; however, there should be 50% reduction in percentage of lymphoma cells

Progressive Disease (PD): For those with > 25% increase in SPD on CT or MRI, Deauville score 4 or 5 on FDG-PET with increase in lesional uptake from baseline, or development of new morphologic evidence of disease in BM

Stable Disease (SD): Neither sufficient shrinkage to qualify for PR nor sufficient increase to qualify for PD, taking as reference the smallest sum diameters while on study.

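### Aim 1.2.5 can count relapsed patients already in CR from rituximab as LMP-TC responders, and the rituximab-dose test in 9.4 does not fit Cohort C

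*Combined protocol and SAP*

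**What the plan says.** **Response to LMP-TC (Aim 1.2.5).** Section 1.2 describes the population as "newly diagnosed (without complete response to Course RTX1), refractory, and relapsed children and young adults"; the condition about complete response is attached to newly diagnosed patients only. For Cohort B, 4.1.2.2 states: "All relapsed patients will be assigned to Arm LMP-TC after induction regardless of response". Section 9.4 states: "Any eligible patient who receives at least one dose of LMP-specific T cells will be considered evaluable for Aims 1.2.5". Section 9.3 classifies response by "comparing disease evaluation at the Week 6 of LMP-CT1 evaluation to the baseline of disease evaluation at the Week 3 evaluation", for all cohorts together and for each one, and adds: "Patients with CR or PR will be considered responders".

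**Response criteria.** For CR, 10.2.7.1 says "CT or MRI should be free of residual mass or evidence of new disease". Section 10.2.4.2 restricts response evaluability: "Only those patients who have measurable disease present at baseline", with at least one dose of protocol therapy. It does not say which baseline. Eligibility (3.2.2.3) is wider: "There must be evaluable disease at study entry either by imaging or by serial endoscopic biopsies".

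**Cohort C.** The Week 3 evaluation belongs to Induction and to non-refractory patients (10.2.1). Cohort C has no Induction, but 4.4.2, 10.2.3 and 10.2.6 require a pre-treatment disease evaluation.

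**EFS, OS and PFS (Aims 1.2.3, 1.2.4, 1.2.6).** Section 9.4 makes an eligible patient evaluable after one or more doses of RTX, the same rule as for Aim 1.2.2. It does not say whether RTX given before enrollment counts. Cohort C receives no RTX on protocol and must have had at least three doses in the 90 days before enrollment (3.2.5). The aims name refractory patients, and 9.3 asks for Kaplan-Meier estimates overall and by cohort. For Aim 1.2.8, 9.4 uses all eligible patients.

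**The concern.** The response rate to LMP-TC is meant to describe what the T cells achieve. A relapsed patient whose disease has cleared on three doses of rituximab has nothing left for the T cells to clear. If that patient stays clear for six more weeks and is counted as a T-cell responder, the Cohort B rate and the pooled rate include responses produced by rituximab. The rate is biased upward whenever remissions persist more often than diseased patients respond.

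The survival question is about who is in the analysis. A rule based on a rituximab dose does not describe a cohort that enters the trial after rituximab and is treated only with T cells.

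Section 2.2 says the pilot is meant to enable later randomized studies, so these estimates may inform them. With about 30 T-cell patients, a few patients counted one way or the other are visible in the rate.

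**Working it through.** **No stated figure to reproduce.** The plan gives no precision or target for these aims. The primary rule (at least 23 of 30, with the look at 15) reproduces as an exact two-stage binomial: 0.7531 at a true rate of 80% and 0.0424 at 60%, against the stated 75.3% and 4.2%. Nothing below touches it.

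**Part 1: a Cohort B patient in CR at Week 3 and still in CR at Week 6.**

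- Sections 4.1.2.2, 9.4 and 9.3 in turn: assigned to LMP-TC, evaluable after one dose, in CR at Week 6, hence a responder. Aim 1.2.5 does not remove the patient.
- Section 10.2.4.2 with the Week 3 baseline of 9.3: no measurable disease at baseline, hence not evaluable.
- Section 10.2.4.2 with a study-entry baseline: evaluable if disease was measurable at entry, hence a responder.
- Under either baseline, 10.2.4.2 is narrower than 9.4, and it omits patients whose disease can be assessed only by endoscopy. Those patients are eligible under 3.2.2.3, and 10.2 provides for assessing them by endoscopy and biopsy. No passage says which rule prevails.

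**Part 2: Cohort C baseline.** Section 9.3 names only Week 3, which Cohort C lacks. The required pre-treatment evaluation has no rival.

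**Part 3: the RTX test in 9.4.**

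- Protocol RTX only: no Cohort C patient is evaluable for EFS, OS or PFS, against the aims and the by-cohort estimates in 9.3.
- Prior RTX included: every eligible Cohort C patient passes through 3.2.5, even with no T-cell dose. Never-treated patients go off study under 8.2(f). This reading would also admit Cohort C to Aim 1.2.2, which 9.3 limits to Cohorts A and B.
- On either reading, the EFS and OS tests of Aim 1.2.8 use a differently defined population from the EFS and OS estimates.

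**Size of Part 1.** All inputs are assumptions; the first has no source in the documents.

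- nB, Cohort B patients among 30 treated: 5 to 10.
- c, share of Cohort B in CR at Week 3: 14/49 = 29% (the cited German three-dose rituximab trial; 11/49 = 22.4% agrees with the 22.5% in 2.4.2) to 60% (complement of the 40% in 9.1). The 60% is for newly diagnosed patients. Applying either figure to relapsed patients is itself an assumption.
- m, share of those still in CR at Week 6: 80% to 100%.
- r, true response rate in patients with disease: 64%, the 5-week rate of the cited third-party T-cell trial (2.5.4). This is closer to the Day 36-41 assessment than that trial's six-month rate of 52%.

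Counting the CRs, the Cohort B rate is c·m + (1 − c)·r. Excluding them, it is r. So the Cohort B rise is c·(m − r) and the pooled rise is (nB/30)·c·(m − r). At r = 0.64, in percentage points:

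| c | m | Cohort B | Pooled, nB = 5 | Pooled, nB = 10 |
|---|---|---|---|---|
| 14/49 | 0.8 | 4.6 | 0.8 | 1.5 |
| 14/49 | 1.0 | 10.3 | 1.7 | 3.4 |
| 0.60 | 0.8 | 9.6 | 1.6 | 3.2 |
| 0.60 | 1.0 | 21.6 | 3.6 | 7.2 |

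At r = 0.52 the ranges are 8.0 to 28.8 points in Cohort B and 1.3 to 9.6 pooled. Cohort A has no inflation, since its Week 3 CRs go to Arm RTX, and neither has Cohort C.

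Example: 10 Cohort B patients, 6 in CR at Week 3 and all maintained, 2 of the other 4 responding. Counted: 8/10 = 80% (exact 95% CI 44% to 97%). Excluded: 2/4 = 50% (7% to 93%).

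**The case against.** The case against Part 1 is a good one. Section 9.3 separates two baselines, study entry for Aim 1.2.2 and Week 3 for Aim 1.2.5. Put Week 3 into 10.2.4.2 and the patients in CR are not response-evaluable. The CR definition also opens by requiring that disease disappear, and a patient without disease at Week 3 has none to lose. This makes exclusion a strong reading. It does not settle the matter: 9.4 sets its own rule for this very aim, by one dose alone, and the two rules give different denominators.

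It can also be said that the size is assumed, that it lies inside sampling error (18/30 has an exact 95% CI of 40.6% to 77.3%), and that no decision depends on the rate. All true. But a bias that a definition can remove is not excused by a wide interval. Reporting by cohort helps in part: a reader can pool Cohorts A and C for an unaffected rate, and the Week 3 CR count signals the problem in Cohort B. The Cohort B rate among patients with disease still cannot be recovered without cross-classifying the two evaluations.

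Part 2 is a missing cross-reference. A reader might infer that response in Cohort C cannot be assessed; the documents do not support that, because the evaluation is required.

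On Part 3, a reader might infer that Cohort C is dropped from the survival analyses. That does not follow, since 9.4 does not say protocol RTX, and the aims and 9.3 plainly intend Cohort C to be included. If prior RTX counts, the extra never-treated patients add little follow-up, so the practical effect is small. The rule still needs correcting, because one reading contradicts the aims and the other admits patients by an eligibility condition instead of by treatment.

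**Conclusion.** The point holds for secondary estimation aims only. Sections 9.3 and 9.4, followed as written, credit LMP-TC with remissions that rituximab produced in Cohort B; 10.2.4.2 contradicts 9.4 without resolving this. The RTX test in 9.4 does not fit Cohort C on either reading. The Cohort C baseline gap is minor.

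The size is not derivable from the documents. With 5 to 10 Cohort B patients among 30, 29% to 60% of them in CR at Week 3, 80% to 100% of those CRs maintained and a true rate of 64%, the pooled rate rises by about 1 to 7 points and the Cohort B rate by about 5 to 22. No size is given for the survival part.

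Two stronger conclusions are tempting. One is that the reported rate will certainly be inflated; it will not be if the analyst applies 10.2.4.2 with the Week 3 baseline. The other is to quote the larger figures, 9.6 points pooled and 28.8 in Cohort B; those need the six-month rate of 52%, which matches the timing of the assessment less well. The primary endpoint, sample size and power are not affected.

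**What to change.** **Section 9.3.** Define the Aim 1.2.5 baseline as the last disease evaluation before Day 0 of LMP-TC1: Week 3 for Cohorts A and B, the pre-treatment evaluation for Cohort C. Limit the denominator to patients with disease by imaging or endoscopy at that baseline. Report Cohort B patients in CR at Week 3 separately, as 'CR maintained' or not.

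**Sections 9.4 (Aim 1.2.5) and 10.2.4.2.** Align both with this: name the baseline and admit disease evaluable by endoscopy.

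**Section 9.4 (survival aims).** For Aims 1.2.3, 1.2.4 and 1.2.6, replace the RTX condition with one or more doses of protocol therapy, RTX or LMP-TC. Keep RTX for Aim 1.2.2. Use the same population for the EFS and OS tests of Aim 1.2.8. Report how many eligible Cohort C patients were never treated.

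**Cost.** Wording only; the data are already collected. There are two downsides. The Cohort B denominator shrinks and its interval widens, as in the example above, although the maintained CRs are still shown. Never-treated Cohort C patients leave the survival estimates, while unmatched Cohort A and B patients stay in through their Induction rituximab, so comparisons between cohorts need that caution. The Abstract expects products to cover more than 90% of eligible patients, so loss for want of a match should be under about 10% of Cohort C, plus any untreated for other reasons. These patients already meet 8.2(f).

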## 2.4 Previous Studies in PTLD

### 2.4.1 Cyclophosphamide/Prednisone/Rituximab (CPR) Therapy

The Children's Oncology Group (COG) conducted a phase 2 study of low dose cyclophosphamide ( $600 \text{ mg/m}^2$ , day 1), prednisone (1mg/kg/dose twice daily, days 1-5) and RTX ( $375 \text{ mg/m}^2$ , days 1,8,15 in Cycles 1-2 only) for six cycles in 55 pediatric patients with EBV positive CD20 positive PTLD from 23 centers. 73% of patients had monomorphic disease and 20% had polymorphic disease. Three patients (7.5%) who had more than one site biopsied were found to have both mono- and polymorphic disease in separate locations. Early treatment response rate (CR or PR after the first two cycles of chemotherapy) was 72%. 29 patients achieved a CR by the end of therapy and an additional eight patients of twelve patients with residual disease at the end of therapy achieved a CR post-therapy without any further therapy. The two year event-free survival was 71% and the two-year overall survival was 83%. Ten patients died, seven due to PTLD and three due to infection during therapy.

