For cytokine release syndrome and graft versus host disease, the analytic unit for monitoring for protocol-specific toxicities will be the patient-course. Each course where the patient receives the agent or where a protocol-specific toxicity event is observed will be considered in the analysis. We will assume a beta prior distribution with  $\alpha = 0.6$  and  $\beta = 1.4$  and an unacceptable toxicity rate of  $p_0 = 30\%$ . At least once per month, we will calculate the posterior probability (given the data) that the probability of protocol-specific toxicity exceeds the 30% threshold, *i.e.*,  $P(p > 0.3 | \text{Data})$ . If there is a posterior probability of 80% that the toxicity rate is at least 30%, then accrual will be suspended pending review by DSMC. Examples of situations in which this rule will indicate protocol-specific toxicities have been noted and are presented below:

Number of failures	Number of patient-cycles
2	3
3	6
4	8
5	11
6	14
7	17
8	20
9	23
10	26
11	29
12	32
13	35
14	38

Interim monitoring will also be performed to watch for a 20% progression rate at week 10 in newly-diagnosed patients and a 40% progression rate at week 10 for relapsed and refractory patients. For newly-diagnosed patients, the beta parameters will be  $\alpha = 0.52$  and  $\beta = 2.08$ ; and for relapsed and refractory patients the beta parameters will be  $\alpha = 1.04$  and  $\beta = 1.56$ ; if there is a posterior probability of 80% that the progression rate at week 10 is at least 20% for newly-diagnosed patients or 40% for relapsed/refractory patients, then accrual for the respective cohort or cohorts will be suspended pending review by the DSMC. The stopping rule will be triggered as described in the following table:

Number of failures	Number of newly-diagnosed patients	Number of relapsed/refractory patients
2	4	2
3	8	4
4	12	6
5	16	8

6	20	11
7	24	13
8	29	15
9	33	17
10	38	19

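### The week-10 suspension rule monitors progression only and does not say how a death before week 10 without documented progression is counted; unless it counts as a failure, the rule triggers less often

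*Combined protocol and SAP*

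**What the plan says.** Section 9.3 describes the rule: "Interim monitoring will also be performed to watch for a 20% progression rate at week 10 in newly-diagnosed patients". The limit for the relapsed/refractory group is 40%. The priors are Beta(0.52, 2.08) and Beta(1.04, 1.56). Accrual to the cohort or cohorts concerned is suspended for DSMC review "if there is a posterior probability of 80% that the progression rate at week 10 is at least 20% for newly-diagnosed patients"; the same trigger applies at 40% in the relapsed/refractory group. A table of failures against numbers of patients follows ("The stopping rule will be triggered as described in the following table"). The general formula earlier in 9.3 uses x events among n observations.

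Three things are not stated: what a failure is for this rule, who counts as an observation at week 10, and what happens to a patient who dies before then. Section 9.4 defines evaluability for the aims, not for this rule. Section 10.2.7.1 defines progressive disease by imaging, PET or marrow findings.

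Elsewhere the plan treats death as an event in its own right. PFS in 9.3 is "time to first occurrence of progression or death (events"), and Section 10.2.9 says the same.

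**The concern.** A patient who dies at week 6 of an infection, before the response scan, has no observable progression status at week 10. As worded, the rule gives no basis for counting that patient as an event, because the monitored quantity is the progression rate. Leaving the death in n as a non-event lowers the posterior. Dropping it from n leaves progression among the remaining patients as the only signal. Either way, a run of early deaths would not push the rule towards suspension.

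This is a real-time safeguard in small cohorts. The first table rows are 2 failures in 4 newly diagnosed patients and 2 in 2 relapsed or refractory patients, so the classification of one patient can decide whether accrual is suspended. Two people applying the same text to the same data could reach opposite decisions.

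**Working it through.** **Inputs.** Priors, limits (p0 = 0.20 and 0.40), the 0.80 trigger and the boundary table are from Section 9.3. The early rate of death without progression is not in the documents. The nearest figure is in Section 2.4.1, on the earlier chemotherapy-rituximab study of 55 patients: "Ten patients died, seven due to PTLD and three due to infection during therapy". That gives 3/55 = 5.5% infection deaths, which is not a week-10 rate, so 1% and 2% are shown as well.

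**Formula.** P(p > p0 | x, n) = 1 − F(p0; α + x, β + n − x), where F is the beta distribution function.

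**The plan's own table.** For each x from 2 to 10, the largest n with a posterior of at least 0.80 was found. All 18 entries reproduce. Examples: newly diagnosed 4/12 gives 0.816 and 4/13 gives 0.774; relapsed/refractory 5/8 gives 0.868 and 5/9 gives 0.794. The boundary arithmetic is correct.

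**Direction.** With x progressions and D deaths without progression among n patients, the posteriors are:
- non-event: Beta(α + x, β + n − x)
- excluded: Beta(α + x, β + n − D − x)
- failure: Beta(α + x + D, β + n − D − x)

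Exclusion lowers the second parameter relative to non-event, and failure raises the first relative to exclusion. The posterior probability therefore always rises in that order.

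**Single-death examples (trigger 0.80).**

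| Data | Non-event | Excluded | Failure |
|---|---|---|---|
| Relapsed/refractory, 4 progressions + 1 death in 8 | Beta(5.04, 5.56): 0.683 | Beta(5.04, 4.56): 0.780 | Beta(6.04, 4.56): 0.868 |
| Newly diagnosed, 4 progressions + 1 death in 13 | Beta(4.52, 11.08): 0.774 | Beta(4.52, 10.08): 0.816 | Beta(5.52, 10.08): 0.909 |

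In the first row only the failure reading suspends. In the second, only the non-event reading does not.

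**Chance of triggering.** This is an exact recursion with a look after every patient, up to the last table row (38 newly diagnosed, 19 relapsed/refractory). The per-patient event probability is the progression rate a if deaths are non-events, and a + d if they are failures, where d is the rate of death without progression by week 10. The look schedule, the horizon, a and d are assumptions.

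| Group | Non-event | Failure, d = 1% | Failure, d = 2% | Failure, d = 5.5% |
|---|---|---|---|---|
| Newly diagnosed, a = 15%, N = 38 | 23.2% | 27.1% | 31.4% | 47.6% |
| Relapsed/refractory, a = 35%, N = 19 | 30.8% | 33.3% | 35.8% | 45.1% |

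Exclusion lies between and close to the non-event figure: 24% and 26% for newly diagnosed at d = 2% and 5.5%, and 32% and 35% for relapsed/refractory.

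**The case against.** A reader might infer that the plan scores an early death as a success. The documents do not support that. No section says so, failure is undefined, and exclusion from n, or even counting the death as a failure, is not ruled out.

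Several kinds of early death are also handled elsewhere:
- Section 9.3 suspends enrollment for review after any known or suspected allograft failure or rejection.
- Section 9.5 counts a death on protocol therapy as a toxicity event if it is at least possibly related to therapy.
- Section 11.4.3 has death from progressive disease reported as Grade 5 disease progression, so such deaths would probably be recognised as progression.
- Section 12.2 has the DSMC review interim toxicity and outcomes.

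This leaves a narrow residual: deaths not due to PTLD, not judged related to therapy, and not involving graft failure or rejection. An infection death judged unrelated is the clearest case.

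The 5.5% figure comes from a six-cycle regimen containing chemotherapy, whereas protocol therapy here has none and entry excludes fulminant PTLD and severe concurrent infection. It may well be too high. The scenarios also straddle the limits: 15% + 5.5% = 20.5% and 35% + 5.5% = 40.5%, so progression alone is below p0 and the combined event just above. Part of the gap therefore arises because the combined event is broader. A progression-only rule with a 20% limit is not malfunctioning when it stays quiet at 15% progression.

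All of this stands, and it limits the size of the point. It does not supply the missing definition. General DSMC review does not replace a prespecified trigger, and adverse-event coding is not stated to feed the week-10 count.

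**Conclusion.** The concern holds as a gap in the definition with a known direction. The rule monitors progression only and is silent on deaths before week 10 without documented progression. Both ways of not counting them make suspension less likely than counting them as failures. One such death can change the decision, and that conclusion needs no assumed death rate.

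The effect on the overall chance of triggering does rest on assumed rates. Between non-event and failure, the difference for newly diagnosed patients at 15% progression is about 4 points at 1% deaths (27.1 − 23.2), 8 at 2% (31.4 − 23.2) and 24 at 5.5% (47.6 − 23.2). For relapsed/refractory patients at 35% progression it is about 2 to 14 points (33.3 − 30.8 up to 45.1 − 30.8). If early deaths of this kind are rare, the practical effect is small. The change is still worth making, because this is a real-time accrual safeguard in small cohorts.

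**What to change.** In Section 9.3, define failure for both week-10 rules as progression or death from any cause by week 10, and state that patients who die before week 10 stay in n. The same sentence should say when the ten weeks start, which 9.3 does not. List deaths without progression separately in the DSMC report, so that the committee can see what drove a trigger.

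The sponsor should also confirm that the 20% and 40% limits and the priors, now stated for progression, are intended for the combined event. If they are, the boundary table is unchanged and only the count of failures differs. If not, the limits and priors need resetting and the table recalculating.

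The cost is a sentence or two in 9.3 and somewhat more frequent suspensions for DSMC review.
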